## TRIAL OVERVIEW

**Title** Vitamin C, Hydrocortisone, and Vitamin B1 in Sepsis and Septic Shock – A Randomized, Double-Blind, Placebo-Controlled Trial (The ACTS Trial)

Clinical Trials Number	NCT03389555
Sources of monetary or material support	Open Philanthropy Project ( https://www.openphilanthropy.org/ )
Study Sites	12-sites in the United States
Condition studied	Sepsis and septic shock
Interventions	Vitamin C (1.5g every 6 hours x 4-days), hydrocortisone (50mg every 6 hours x 4-days), and Vitamin B1 (100mg every 6 hours x 4-days)
Comparator	Placebo
Inclusion criteria	

• Adult participant (age ≥ 18 years)

• Suspected (cultures drawn and antibiotic given) or confirmed (via culture results) infection

• Receiving vasopressor (norepinephrine, phenylephrine, epinephrine, dopamine, vasopressin, or angiotensin II)

Exclusion criteria	

• Member of a protected population (pregnant, prisoner)

• Known history of kidney stones within the past 1 year

• End stage renal disease (ESRD) requiring dialysis

• Known history of G6PD deficiency

• Known history of Hemochromatosis

• Comfort Measures Only status

• Anticipated death within 24-hours despite maximal therapy (as determined by the enrolling physician)

• Receiving supplemental vitamin B1 in a dose greater than that contained in a multivitamin (<2mg)

• Clinical indication for steroids (e.g. chronic use) as determined by the clinical team providing this drug

• Clinical indication for ascorbic acid supplementation in any form

• Clinical indication for vitamin B1 as determined by the clinical team providing this drug

• Known allergy to vitamin C, hydrocortisone, or vitamin B1

Study type	Interventional Allocation: Randomized (1:1) Intervention model: Parallel group Masking: Double-blind
Target sample size	200 Participants (100/arm)
Primary outcome	Change in the Sequential Organ Failure Assessment (SOFA) score between enrollment and 72-hours
Key secondary outcomes	Incidence of renal failure during index ICU stay 30-day mortality

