### **2.2 Allocation**

Participants will be randomized in a 1:1 ratio to either the combination of vitamin C, hydrocortisone, and vitamin B1 or placebo in blocks with random sizes of 2 or 4. The randomization will be stratified according to site. An independent statistician will create the randomization list using a random number generator. The complete list will only be shared with an independent pharmacy consultant, who will not be involved in clinical care. The pharmacy consultant and the independent statistician will both store the randomization list. The research pharmacy at each enrolling site will receive a site-specific randomization list.

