## 6. SAMPLE SIZE CALCULATION AND STATISTICAL ANALYSIS PLAN

### 6.1 Sample size calculation

The study has been powered to have at least 80% power for the primary outcome and all key secondary outcomes as follows:

**SOFA Score:** Based on preliminary data, we conservatively anticipate a decrease in SOFA score of 6 (standard deviation [SD]: 4) in the treatment group and 4 (SD: 2) in the placebo group. With these estimates, enrollment of **200 participants (100/arm)** at an alpha of 0.05 and using a t-test with unequal variance, the trial will provide > 99% power to detect a statistical significant difference between groups.

**Kidney Injury:** Based on preliminary data from our study of vitamin B1 in septic shock, we anticipate that 30% of participants in the treatment group and 55% in the placebo group will have renal failure which will result in a 94% power for this outcome. This calculation and following calculation were performed using the Fisher's exact test.

**Mortality:** Based on preliminary data, we anticipate that the control group will have a mortality of 40%. We estimate a treatment effect of 50% (risk ratio: 0.50) resulting in a mortality of 20% in the treatment group. With these estimates, 182 participants will lead to 80% power. To further increase

the trial's power and due to potential loss-to-follow-up, we will aim to enroll 200 participants. These estimates are conservative compared to the Marik et al. study which found a treatment effect corresponding to a risk ratio of 0.21 which persisted in adjusted analysis.

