## 6.2 Statistical analysis plan

### 6.2.1 General considerations

The statistical analyses and reporting will adhere to the CONSORT guidelines. All tests will be two-sided, a p-value  $< 0.05$  will be considered significant, and all confidence intervals will have 95% coverage. All analyses will be conducted on a modified intention-to-treat basis only including participants receiving at least the first dose of the study medications. In a double-blind trial, this approach is unbiased while increasing precision. The two groups will be compared in relation to baseline characteristics using descriptive statistics.

The persons conducting the statistical analysis will be blinded to the randomized allocation. Groups will be designated as "A" and "B" until all pre-specified analyses are performed and shared with all authors and the Data Safety Monitoring Board.

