### 6.2.2 SOFA score and renal failure

The change in SOFA score will be calculated and compared between groups using the Wilcoxon Rank Sum test (if the change is not normally distributed) or by a t-test if the change is approximately normally distributed. Fisher's exact tests will be used to compare the incidence of renal failure during the index ICU stay.

If a participant expires prior to the 72-hour time point, SOFA scores will be imputed based on a pre-defined plan as follows. If a participant expires before 24-hours has elapsed, a 20% increase from baseline will be imputed. If a participant expires between 24-hours and 48-hours, a 15% increase from the 24-hour time point will be imputed. If a participant dies between 48-hours and 72-hours, a 20% increase from the 24-hour time point will be imputed. Sensitivity analyses will be performed using various other imputation techniques. Specifically, we will perform 1) a sensitivity analysis in which the worst possible SOFA score (score of 24) is imputed for those participants who expire, 2) a sensitivity analysis in which the last SOFA score for participants who expire will be carried forward, and 3) a sensitivity analysis in which only those patients who survive to 72-hours are included. These sensitivity analyses were chosen to model 'worst-possible' and 'best-possible' scenarios. For the secondary outcome of renal failure, participants who expire during their ICU stay will be assessed to have developed renal failure if they demonstrated any degree of unresolved KDIGO acute kidney injury prior to death. If there was no evidence of acute kidney injury prior to death or if kidney injury had fully resolved, these participants will be assessed as not having developed renal failure.

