### 6.2.3 30-day mortality

Survival until 30 days will be analyzed using survival analysis. Participants lost to follow-up will be censored and the censoring will be assumed non-informative. Results will be presented with Kaplan-Meier curves and the groups compared using the log-rank test. Hazard ratios with 95% confidence intervals will be obtained using Cox's proportional hazards models. The proportional hazards assumption will be verified by visual inspection of the Kaplan-Meier curves and statistically by including a product term (i.e. "interaction") between the treatment group variable and the natural logarithm of time in the model. If the proportional hazards assumption is not met, only the Kaplan-Meier curves and the p-value from the log-rank test will be presented.

Adverse events and other binary outcomes will be presented and analyzed like renal failure.

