### 6.2.4 Additional Secondary Analyses

Both ICU and hospital length of stay will be compared using Wilcoxon Rank Sum tests. Ventilator and shock free days over the first 7-days after enrollment will likewise be compared using the Wilcoxon Rank Sum given that the data will likely be not normally distributed. In these latter two analyses, patients who expire prior to 7-days will be assessed to have 0 ventilator or shock free days if they had died while on a ventilator or vasopressor respectively. The incidence of delirium will be compared using the Fisher's exact test. For the quality-of-life outcome (i.e. 90-day SF-36), the primary analysis will only include patients with available data. As a secondary analysis, multiple imputation will be used to estimate SF-36 scores in all patients not known to be dead at 90 -days.

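### Fisher's exact test for renal failure, delirium and adverse events is valid but conservative at 100 per arm; Boschloo's test would recover some power at no cost in error, and an effect measure should be named

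*Protocol*

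**What the plan says.** Protocol section 6.2.2 states that Fisher's "exact tests will be used to compare the incidence of renal failure during the index ICU stay". The last line of section 6.2.3 adds: "Adverse events and other binary outcomes will be presented and analyzed like renal failure". Section 6.2.4 says: "The incidence of delirium will be compared using the" Fisher's exact test. The SAP repeats all three statements in its sections of the same numbers.

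The sample size section (6.1) used the same test. After giving 94% power for renal failure at 30% vs 55%, it says: "This calculation and following calculation were performed using the" Fisher's exact test, the calculation that follows being the one for mortality.

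On effect measures, section 6.2.3 names a hazard ratio with a 95% interval for 30-day mortality. No risk difference, risk ratio or odds ratio is named for renal failure, delirium or any adverse event. Section 6.2.1 commits the analyses and reporting to CONSORT and says that confidence intervals will have 95% coverage.

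**The concern.** Fisher's test conditions on the total number of events. With two arms of 100 the conditional distribution is coarse, so the attained error lies below the nominal 5%, and furthest below when events are few. The unused error is lost power.

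For safety outcomes that loss runs in the less cautious direction: a real excess is somewhat more likely to be reported as not significant. Section 5.4.2 lists hyperglycemia, hypernatremia, new infection, serious allergic reaction and renal calculus. Section 8.1.2 itself notes that hydrocortisone may raise the risk of hyperglycemia and that some studies found more secondary infection. With no named effect measure, the only analysis actually specified for these events is a p-value. A non-significant p-value does not show how large a harm the data still allow.

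**Working it through.** **Inputs from the documents.** Target "200 Participants (100/arm" (Trial Overview); "Participants will be randomized in a 1:1 ratio" (2.2); "All tests will be two-sided" (6.2.1); alpha 0.05 (6.1 and 6.2.1); renal failure 30% vs 55% with 94% power, and mortality 20% vs 40% with 182 participants for 80% power (6.1).

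**Assumed.** The documents give no expected adverse event rates. The harm scenarios below are illustrations over a range.

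**Method.** All 101 × 101 possible tables were enumerated. Let b(x; n, p) be the binomial probability of x events in n, and pF(x, y) the two-sided Fisher p-value for x vs y events. Then

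P(reject) = Σx Σy b(x; 100, p1) · b(y; 100, p2) · 1[pF(x, y) < 0.05].

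Setting p1 = p2 gives the true type I error; setting p1 ≠ p2 gives power. Boschloo's test uses pF as its statistic and rejects when pF ≤ c, where c is the largest cutoff that keeps the maximum error over all common rates at or below 5%. At 100 per arm c = 0.0638 and the maximum error is 4.96%. Since 0.0638 > 0.05, every table that Fisher's test rejects is also rejected by Boschloo's.

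**Step 1: the plan's own figures.**
- Renal failure, 30% vs 55%, 100 per arm, Fisher: 93.9% (stated 94%).
- Mortality, 20% vs 40%, 182/2 = 91 per arm, Fisher: 80.8% (stated 80%).

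Both reproduce.

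**Step 2: true error at nominal 5%, 100 per arm.** The average planned renal rate is (30% + 55%)/2 = 42.5%.

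| Common event rate | Fisher | Boschloo |
|---|---|---|
| 1% | 0.04% | 0.25% |
| 2% | 0.46% | 1.4% |
| 5% | 2.1% | 2.9% |
| 10% | 2.9% | 3.8% |
| 42.5% | 3.8% | 4.9% |
| 50% | 4.0% | 4.2% |
| Maximum over all rates | 4.0% | 4.96% |

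**Step 3: power, 100 per arm.**

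| Rates | Fisher | Boschloo | Gain (points) |
|---|---|---|---|
| Renal failure, 30% vs 55% (plan) | 93.9% | 95.1% | 1.2 |
| 1% vs 5% (assumed) | 19.4% | 26.6% | 7.2 |
| 2% vs 8% (assumed) | 37.2% | 42.0% | 4.8 |
| 5% vs 15% (assumed) | 58.6% | 63.0% | 4.4 |
| 10% vs 25% (assumed) | 76.2% | 79.2% | 3.0 |
| 15% vs 30% (assumed) | 66.9% | 71.3% | 4.4 |
| 30% vs 45% (assumed) | 53.5% | 58.9% | 5.4 |
| 40% vs 55% (assumed) | 53.0% | 54.2% | 1.2 |

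**Step 4: other replacements.** Fisher's mid-P version and Pearson's chi-square give slightly more power (95.5% each for renal failure), but their maximum error at 100 per arm is 5.6%. Boschloo's test is the one that gains power while holding 5%.

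**Step 5: test and interval together (hypothetical counts).**
- New infections in 14/100 vs 5/100: Fisher p = 0.051, not significant under the 0.05 rule, while Boschloo's test rejects. The risk difference is 9 points, with a 95% Miettinen-Nurminen score interval of 0.9 to 17.8.
- 13/100 vs 5/100: the score interval just excludes zero, but Boschloo's test does not reject.

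The score interval and Boschloo's test can therefore disagree near 0.05. Reading significance off the score interval would also have an error of up to 5.6%.

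**The case against.** The strongest defence is that Fisher's test is valid and was planned for. Its error never exceeds 5%, and its conservatism is already inside the stated 94%. That stands. A reader might infer that the renal power is wrong or that the outcome is underpowered; the 94% reproduces, and the gain there is 1.2 points.

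A reader might also infer that the trial will report no effect size for these outcomes. The documents do not say that. They are silent on the measure, while section 6.2.1 commits to CONSORT and to 95% intervals. The gap is one of pre-specification. Nor is Fisher's method inherently limited to a p-value: inverting the conditional test gives an exact interval for the odds ratio.

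Third, Boschloo's test does not remove the conservatism for rare events. Its own error is 0.25% at a 1% rate and 1.4% at 2%. Low power for rare harms comes mainly from the sample size: at 1% vs 5%, Boschloo's test reaches only 27%, and the most liberal test tried (chi-square) 37%. The documents also do not show that the listed harms are rare.

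Finally, it is tempting to conclude that participants are less protected during the trial. The DSMB reviews data after every 50 participants with no formal statistical criteria for termination (9.2), so monitoring does not depend on this p-value. All four points hold and limit the size of the concern. None gives a reason to prefer Fisher's test over one that rejects whenever it does and still holds 5%.

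**Conclusion.** The point holds as an efficiency improvement of minor weight. The plan uses a valid test whose true error at 100 per arm is between almost nil (0.04% at a 1% event rate) and about 4.0%. Boschloo's test uses more of the permitted 5% and cannot lose power. The gain is 1.2 points for renal failure at the planned rates. In the harm scenarios run it is mostly 3 to 7 points, and 1.2 points at 40% vs 55%.

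The error figures rest on exactly 100 per arm. Unequal arms, participants not assessed for delirium, or a change in the enrollment target would shift them slightly. The safety power figures rest on assumed event rates. Separately, an effect measure should be named for these outcomes; for rare harms, where any test has little power, the interval will be more informative than the p-value.

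**What to change.** In sections 6.2.2 to 6.2.4 of the protocol and SAP, replace Fisher's exact test with Boschloo's exact unconditional test (two-sided, 0.05) for renal failure, delirium, adverse events and other binary outcomes, computed for the realised arm sizes. In the same sections, name the risk difference with a 95% interval as the effect measure, and for adverse events present the interval first.

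Because a score interval and Boschloo's test can disagree near 0.05, add one of two sentences. Either the interval is obtained by inverting the same unconditional exact test, or the Boschloo p-value governs significance and the score interval is descriptive.

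The cost is a few lines of text and standard software. No outcome loses power, the error stays at or below 5%, and data collection does not change. The 94% in section 6.1 can remain as a slightly conservative figure or be updated to 95%. If the sponsor prefers to keep Fisher's test, naming the effect measure and interval is still worth doing.

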#### **3.3 Exclusion criteria**

Exclusion criteria:

- 1) Member of a protected population (pregnant, prisoner)
- 2) Known history of kidney stones within the past 1 year (not including incidentally noted stones noted on imaging studies)
- 3) End stage renal disease requiring dialysis (hemodialysis or peritoneal dialysis)
- 4) Known history of G6PD deficiency
- 5) Known history of Hemochromatosis
- 6) Comfort Measures Only status
- 7) Anticipated death within 24-hours despite maximal therapy (as determined by the enrolling physician)
- 8) Receiving supplemental vitamin B1 in a dose greater than that contained in a multivitamin (<2mg)
- 9) Clinical indication for steroids (e.g. chronic use) as determined by the clinical team providing this drug
- 10) Clinical indication for ascorbic acid supplementation in any form
- 11) Clinical indication for vitamin B1 as determined by the clinical team providing this drug
- 12) Known allergy to vitamin C, hydrocortisone, or vitamin B1

Justification of Inclusion and Exclusion Criteria: The inclusion criteria were chosen to isolate a septic participant population with high risk of organ injury and death. The exclusion criteria were chosen to minimize the risk of potential harm and to ensure that participants enrolled do not already have chronic end-stage renal failure with a high likelihood of early need for renal replacement therapy. By evaluating this high-risk population (i.e., most likely to die), we will target those most likely to benefit and therefore increase the probability of showing efficacy.

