### 5. OUTCOMES

#### 5.1 Definitions

##### 5.1.1 Primary Outcome

The primary outcome will be the absolute change in the Sequential Organ Failure Assessment (SOFA) score from enrollment (time=0) to 72 hours after drug administration. The SOFA score will be defined using a modification in which the SaO2/FiO2 ratio is substituted for the PaO2/FiO2 ratio as has been previously described. This modified score will be used so that participants without an existing arterial catheter can be spared arterial puncture.

Points	SaO 2 */FiO 2 §	Blood Pressure	GCS 	Bilirubin (mg/dL)	Creatinine (mg/dL)	Platelets (x10  µL)
1	<400	< 70 mm/Hg	13–14	1.2–1.9	1.2 – 1.9	<150
2	<326	dopamine ≤ 5 µg/kg/min or dobutamine (any dose)	10–12	2–5.9	2.0 – 3.4	<100
3	<236 (and receiving invasive or non-invasive mechanical ventilation)	dopamine > 5µg/kg/min, epinephrine/norepinephrine ≤ 0.1 µg/kg/min	6–9	6–11.9	3.5 – 4.9 Or UOP † <500ml/day	<50
4	<151 (and receiving invasive or non-invasive mechanical ventilation)	dopamine > 15, epinephrine/norepinephrine > 0.1 µg/kg/min	<6	>12	> 5.0 UOP † <200ml/day Or receiving renal replacement therapy	<20

\*SaO2=Oxygen saturation (%); § = Fraction of inspired oxygen (%); || = Glasgow Coma Scale; † = Urine Output

FiO2 will be determined by using either the set FiO2 (for patients receiving invasive or non-invasive mechanical ventilation) or by adding 3% FiO2 for each liter/minute of supplemental oxygen added up to 100% FiO2 (for patients not receiving mechanical ventilation). Patients with an SaO2/FiO2 ratio <236 who are not receiving invasive or non-invasive mechanical ventilation, will be assigned a score of 2.

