## Sample Size Adjustment

If after 100 patients are enrolled, the overall change in SOFA score is less than anticipated in the above power analysis and/or the renal failure event rate or mortality rate is lower than predicted, the enrollment target of 200 patients may be adjusted accordingly so as to improve power for the primary outcome and all key secondary outcomes at the end of the trial period. Specifically, we will aim to maintain  $\geq 90\%$  power to detect a 2-point difference in  $\Delta$ SOFA score (using variance seen for the full cohort) and  $\geq 80\%$  power to detect a 50% treatment effect on mortality. Whether to increase the study sample size, and the degree of sample size increase, will be decided on by the blinded Steering Committee who will not have access to data stratified by treatment group. The Steering Committee will take into account logistical and financial considerations when updating the enrollment target.

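### Deaths between 24 and 72 hours are imputed from the 24-hour SOFA score with no floor at enrollment, so the primary analysis can score a death as improvement

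*Protocol*

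**What the plan says.** Protocol section 5.1.1 defines the primary outcome as the "absolute change in the Sequential Organ Failure Assessment (SOFA) score from enrollment (time=0) to 72 hours". Section 6.2.2, repeated in the SAP, sets three rules for participants who die before the 72-hour score:

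- Before 24 hours: "If a participant expires before 24-hours has elapsed, a 20% increase from baseline will be imputed".
- 24–48 hours: "If a participant expires between 24-hours and 48-hours, a 15% increase from the 24-hour time point will be imputed".
- 48–72 hours: "If a participant dies between 48-hours and 72-hours, a 20% increase from the 24-hour time point will be imputed".

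The first rule starts from the enrollment score and the other two from the 24-hour score. None has a floor at the enrollment score or an upper limit. Three sensitivity analyses follow: one in which "the worst possible SOFA score (score of 24) is imputed for those participants who expire", one carrying the last score forward, and one restricted to 72-hour survivors.

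**The concern.** The outcome is measured from enrollment, but for deaths after 24 hours the penalty is measured from the 24-hour score. If a participant improves over the first day and then dies, the percentage increase may not bring the score back to the enrollment level, and the death enters the primary test as a favorable result. A death before 24 hours cannot do this. The plan evidently means to penalize death, and the later branches can fail to.

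The trigger is realistic. Participants must be on a vasopressor at first dose (section 4.3). In the section 5.1.1 table, norepinephrine or epinephrine scores 3 or 4 points, and the same component scores 0 or 1 once vasopressors are off. Weaning alone can therefore lower the score by 2 to 4 points. The before-and-after study in section 1.3 reports shock reversal at 18.3 hours on treatment against 54.9 hours without, which lie on opposite sides of the 24-hour anchor. A difference between arms in the anchor is thus plausible on the plan's own hypothesis. The rule would then credit the drug with a transient fall in people who died, and could mute an excess of early deaths.

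There is also a smaller gap. Without a cap, imputed scores can exceed 24, which the plan itself calls the worst possible score.

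**Working it through.** **The plan's power figure.** Section 6.1 assumes falls of 6 (SD 4) and 4 (SD 2), 100 per arm, two-sided 0.05. The standard error is √(16/100 + 4/100) = 0.447, and 2/0.447 = 4.47. Power is 99.4% by the normal approximation and 99.3% by the Welch t-test (df 145.6), which agrees with the stated figure of over 99%. That calculation does not model deaths, so this point leaves it unchanged.

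**Break-even.** Let S0 be the enrollment score, S24 the 24-hour score, and f = 1.15 (death at 24–48 h) or 1.20 (48–72 h). The imputed change is f × S24 − S0, which is negative when S24 < S0/f.

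- 24–48 h: 1/1.15 = 0.870, a fall of more than 13.0%.
- 48–72 h: 1/1.20 = 0.833, a fall of more than 16.7%.

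For enrollment scores of 8 to 16, a fall of 2 or 3 points is enough. Illustrative scores:

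| S0 | S24 | Death 24–48 h | Death 48–72 h | Death before 24 h |
|---|---|---|---|---|
| 12 | 12 | +1.8 | +2.4 | +2.4 |
| 12 | 10 | −0.5 | 0.0 | +2.4 |
| 12 | 9 | −1.65 | −1.2 | +2.4 |
| 10 | 8 | −0.8 | −0.4 | +2.0 |

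**Cap.** 1.20 × 21 = 25.2 and 1.15 × 21 = 24.15, both above 24.

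**How often.** The documents give no 24-hour scores. Assume enrollment SOFA of 9 or 12 (SD 3) and a 24-hour change with SD 2.5 (400,000 draws per cell, integer scores). The share of deaths scored as improved is:

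| Mean 24-hour change in those who die | 15% rule | 20% rule |
|---|---|---|
| 0 to −2 | 26.8–62.1% | 20.7–56.4% |
| +1 to +3 | 3.6–19.3% | 2.4–15.7% |

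At 5 such deaths per 100, that is about 0.1 to 3 participants per arm.

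**Effect on the test.** The simulation used 100 per arm, with each death equally likely in either window. It covered 12 settings (enrollment 9 or 12; survivor change −1, −2 or −4; survivor SD 2.5 or 3.5) with 6,000 trials each, for a Monte Carlo error of about 0.3–0.5 percentage points. The proposed rule is min(24, f × max(S0, S24)). Ranges run over the settings.

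*Identical arms* (5% or 10% deaths, mean 24-hour change 0 or −2): Wilcoxon rejection under the plan is 4.3–5.3%, mean about 4.9%.

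*Drug lowers the 24-hour score by 2 points, with no effect on deaths or survivors:*

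| Deaths per arm, 24–72 h | Shift, plan | Shift, proposed | Wilcoxon, plan | Wilcoxon, proposed |
|---|---|---|---|---|
| 5% | 0.11–0.13 | 0.03–0.05 | 4.9–6.0% (mean 5.5%) | 4.3–5.5% (mean 4.9%) |
| 10% | 0.22–0.24 | 0.07–0.09 | 5.8–8.4% (mean 7.1%) | 4.7–5.5% (mean 5.1%) |
| 15% | – | – | 7.4–12.1% | 4.5–6.0% |

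Under the plan, t-test rejection is 5.2–6.5% at 5% deaths and 7.2–9.6% at 10%.

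*Excess deaths on drug, Wilcoxon significant in the harm direction:*

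| Deaths, drug vs placebo | Drug effect at 24 h | Plan | Proposed |
|---|---|---|---|
| 10% vs 5% | none | 4.5–8.2% (mean 6.0%) | 6.1–9.0% (mean 7.6%) |
| 10% vs 5% | 2 points lower | 1.5–4.8% (mean 2.6%) | 5.0–8.9% (mean 6.7%) |
| 20% vs 10% | none | 7.6–19.2% | 12.6–22.9% |
| 20% vs 10% | 2 points lower | 0.7–6.9% | 7.8–20.2% |

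If 24-hour scores rise by 2 in both arms, the gain at 20% vs 10% is small: 13.6–22.1% under the plan and 15.4–23.5% under the proposed rule (4,000 trials per setting).

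For scale, section 6.1 expects 30-day mortality of 40% on placebo and 20% on drug. So 15% per arm within 24–72 hours is an upper scenario, and 20% on drug would use up all of that arm's expected 30-day deaths.

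**The case against.** The case for calling this minor is substantial.

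- **Size.** With identical arms nothing is inflated. At 5% deaths the shift is at most 0.13 points, against a plan that seeks "power to detect a 2-point difference in" the change in SOFA score. Material effects need about 10% or more of an arm to die within a 48-hour window. This stands and limits the severity.
- **Narrow scenario.** The inflated rejection rates need a drug that lowers the 24-hour score in those who die but changes neither deaths nor survivors. If survivors benefit too, rejecting is not an error. This stands for type I error. It does not answer the muted harm signal or the wrong sign.
- **Who dies.** Section 5.2 ties organ failure to mortality, so scores may rise before death, and then few deaths are scored as improved. That is possible, but the documents do not settle it.
- **Harm detection is weak under any rule.** With 10% vs 5% deaths and no 24-hour effect, scoring every death as 24 finds harm only 8.9% of the time. Mortality at 30 days is tested separately, and the DSMB reviews data after every 50 participants. This is true, but with a 2-point lowering the plan's rule takes an already weak signal down to 2.6%.
- **Sensitivity analyses.** Scoring deaths as 24 removes the problem and would make the dependence visible. Carrying the last score forward deepens it (12 to 9 gives −3), and the survivors-only analysis drops the deaths. The primary p-value still comes from the unfloored rule.
- **A bare floor would do.** Using max(f × S24, S0) corrects the sign, and the proposed rule goes further. In a separate run the bare floor left shifts of 0.06–0.08 (5% deaths) and 0.12–0.16 (10%), and mean harm detection of 5.0% rather than 6.7% (10% vs 5%, 2-point lowering). Either rule is defensible. The proposed one treats later deaths as the plan already treats those before 24 hours.
- **Cap.** It bites only from a score of 21 and reduces the penalty: enrollment 24 followed by death would score 0. It is a consistency point only.

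**Conclusion.** The concern holds and should be fixed. That a death at 24–72 hours can be scored as improvement follows from the written rule by arithmetic and needs no assumption. Its frequency and effect do rest on assumptions about 24-hour scores and early deaths. On those used here, about 2–62% of such deaths would be scored as improved, and at 10% deaths a 2-point difference between arms at 24 hours raises mean Wilcoxon rejection by about 2 percentage points. The more serious consequence is that a transient early fall on drug can hide an excess of deaths from the primary test. The effect on the mean is small beside 2 points, and the stated power is not in dispute. Confidence is high in the defect and moderate in its size.

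**What to change.** In section 6.2.2 of both documents, before unblinding:

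1. For deaths at 24–48 and 48–72 hours, apply the stated 15% or 20% to the higher of the enrollment and 24-hour scores. The 12-to-9 example with death at 60 hours then gives 1.20 × 12 = 14.4, a change of +2.4.
2. Cap imputed scores at 24 in all three branches.
3. Keep the current rule as a sensitivity analysis.
4. Optionally, add a rank analysis placing every death before 72 hours below all survivors. This answers a separate question: a death before 24 hours from an enrollment score of 9 scores only +1.8 and can rank ahead of a survivor who worsened more.

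The cost is wording, with no new data. It does change the primary-analysis rule, so it needs a protocol amendment and review at the sites. Early deaths would carry slightly more weight in the mean difference. A rise in the 24-hour score in one arm among those who die would still pass through in part. For 0 against +2 at 10% deaths, the shift is 0.14–0.16 (plan 0.22–0.24) and t-test rejection 5.4–6.5% (plan 6.4–8.6%).
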